## **7.1 Study Subjects**

### **7.1.1 Subject Disposition**

Subject disposition will be presented for the Screened Population. The following will be presented in a disposition table:

- Number of subjects screened
- Number of subjects dosed with OpRegen by cohort and overall (All Treated Population)
- Number and percentage of subjects who terminated prematurely before 1 Year Visit by cohort and overall
- Reason for premature termination before 1 Year Visit by cohort and overall
- Number and percentage of subjects who completed 1 Year Visit by cohort and overall

The number of subjects in the above categories will also be presented in a flow diagram figure.

A table with the number of screen failures and reason for screen failure will be produced.

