1. STUDY SYNOPSIS

Protocol Number

CCN_CT02

Protocol Title

Phase I/IIa Dose Escalation Safety and Efficacy Study of Human Embryonic Stem Cell-Derived Retinal Pigment Epithelium Cells Transplanted Subretinally in Patients with Advanced Dry-Form Age-Related Macular Degeneration (Geographic Atrophy)

Sponsor

Cell Cure Neurosciences Ltd./BioTime, Inc.

Study Centers and Planned Geographical Distribution

Multicenter multinational trial

Clinical Phase

Phase I/IIa study

Investigational Product

OpRegen® is a cell-based product composed of retinal pigment epithelium (RPE) cells, derived from human embryonic stem cells (hESCs) through a process of directed differentiation. OpRegen® can be implanted as a single cell suspension to form a targeted suspension of 50×10^3 to 200×10^3 in a total volume of 50-100 μL in either an ophthalmic

Study Duration

- Screening period of up to [REDACTED].
- Part 1: Eligible subjects will be enrolled into Part 1 of the trial for approximately 52 weeks (up to ± 14 days) for a post-implantation follow up assessment.
- Part 2: Following the successful completion of Part 1 of the study, subjects will continue into Part 2 defined as the long term follow up with evaluations at [REDACTED], [REDACTED].

Study Objectives

Primary Objectives

To evaluate the safety and tolerability of human embryonic stem cell-derived retinal pigment epithelium cells (OpRegen®), transplanted subretinally to subjects with advanced dry age-related macular degeneration (AMD) with geographic atrophy (GA).

Secondary Objectives

To evaluate the preliminary efficacy of OpRegen® treatment by assessing the changes in ophthalmological parameters as measured by various methods of primary clinical relevance.

¹ Refer to Section 2.3 in the Investigator Brochure for more information about the Product Description

[REDACTED]

Study Endpoints

Safety and Tolerability Endpoints

Safety and tolerability of OpRegen® treatment will be assessed by:

- Incidence and frequency of treatment emergent adverse events (AEs)
- Treatment emergent changes in the following variables:
 - Vital signs
 - Hematology/ Blood Chemistry/ Urinalysis
 - Physical examination
 - Ophthalmological evaluations including:
 - ✓ Best Corrected Visual Acuity (BCVA)
 - ✓ Dilated Fundus Exam
 - ✓ Intraocular Pressure (IOP)
 - ✓ Slit Lamp Examination (SLE)
 - ✓ Spectral Domain Optical Coherence Tomography (SD-OCT)
 - ✓ Fluorescein Angiography (FA)
 - ✓ Microperimetry
 - ✓ Fundus Autofluorescence (FAF)

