22.11 TOLERABILITY ASSESSMENTS

Tolerability analysis will be based on the number and percent of subjects who failed to reach the [REDACTED] due to adverse events and overall discontinuation rate. The time to withdrawal due to adverse events and overall discontinuation rate, starting from the day of study IP administration will be presented using Kaplan-Meier curves.

A similar analysis approach will be repeated for the study Part 2 duration.

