## 3.0 STUDY OBJECTIVES AND ENDPOINTS

### 3.1 Study Objectives

#### 3.1.1 Primary Objectives

To evaluate the safety and tolerability of human embryonic stem cell-derived retinal pigment epithelium cells (OpRegen), transplanted subretinally to subjects with advanced dry age-related macular degeneration ([AMD](#)) with geographic atrophy ([GA](#)).

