### Long-term follow-up analysis of safety and efficacy (5 years post-last OpRegen dose)

Final analysis will be performed using data from all subjects with a Year 5 post-treatment assessment.

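### The SAP leaves out the protocol's tolerability analysis (withdrawal for adverse events, with Kaplan-Meier curves, in both parts) without giving a reason, and its disposition table and flow diagram stop at Year 1

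*SAP*

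**What the plan says.** Both documents make tolerability part of the primary objective. SAP 3.1.1 reads "To evaluate the safety and tolerability of human embryonic stem cell-derived retinal pigment epithelium cells", and Protocol 7.2.1 has the same aim.

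Protocol 22.11 says how tolerability is to be analysed. The opening words are "Tolerability analysis will be based on the number and percent of subjects who failed to reach the"; the time point that follows is redacted, and the stated cause is AEs. The section adds the overall discontinuation rate. Time to withdrawal, "starting from the day of study IP administration will be presented using Kaplan-Meier curves", comes next. The section ends: "A similar analysis approach will be repeated for the study Part 2 duration". Protocol 22.7 separately plans a descriptive summary of withdrawals from follow-up, with no one-year limit.

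SAP 7.1.1 sets out one disposition table. Its entries include "Number and percentage of subjects who terminated prematurely before 1 Year Visit by cohort and overall" and "Reason for premature termination before 1 Year Visit by cohort and overall", and completion is counted at the same visit. The flow diagram uses the same categories.

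SAP Section 11 lists Tables 14.1.2 (Time in Study) and 14.1.3 (Early Discontinuations), and Listings 16.1.2 and 16.1.3 on the same subjects. On the long-term analysis, SAP 9.0 says: "Final analysis will be performed using data from all subjects with a Year 5 post-treatment assessment".

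**The concern.** A withdrawal caused by harm is the most direct sign that a treatment was not tolerated, and the protocol chose it as the basis of its tolerability analysis. If the SAP is followed as written, that analysis is not produced for either part. The disposition table and flow diagram, where a reader looks first for attrition, show nothing after Year 1.

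The long-term report could then set one-year retention beside five-year safety results. SAP 3.3 hypothesises that the product is well tolerated, and the reader could not see from the specified summaries how many subjects left during Part 2 because of AEs, or when. Summaries built only on those who reached Year 5 would make this worse, because subjects who left because of harm would be missing from them.

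**Working it through.** There is no stated figure to reproduce. The check sets the two documents side by side.

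**1. Same protocol version.** The SAP's statement of purpose (Section 2.0) says it is based on Amendment 14, which is the protocol reviewed here and contains 22.11. A version difference does not explain the omission.

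**2. Where the one-year cut falls.** Protocol Section 1 says: "Eligible subjects will be enrolled into Part 1 of the trial for approximately 52 weeks". The 1 Year Visit is therefore at or near the boundary between Parts 1 and 2, and the 7.1.1 termination counts cover essentially none of Part 2.

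**3. Element by element.**

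| Protocol element | SAP text | SAP output list (Section 11) |
|---|---|---|
| Number and percent discontinued due to AEs, Part 1 | No tolerability section in 7.1.1 to 7.1.10; reasons before Year 1 in 7.1.1 | Table 14.1.1; Table 14.1.3 by title only |
| Overall discontinuation, Part 1 | 7.1.1, before Year 1 | Table 14.1.1 |
| Kaplan-Meier time to withdrawal, Part 1 | None | None |
| Number and percent discontinued due to AEs, Part 2 | None | Table 14.1.3 by title; period and reasons undefined |
| Overall discontinuation, Part 2 | None | Table 14.1.3 by title; period undefined |
| Kaplan-Meier time to withdrawal, Part 2 | None | None |

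Some Part 1 content can be recovered from 7.1.1. For Part 2 there is a table title and no rule. The curves are missing in both parts.

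**4. What the SAP still covers after Year 1.** SAP 4.1.1 defines total days on study as last study date minus injection date plus 1, with no cap, so Table 14.1.2 can span all follow-up. SAP 7.1.6 tabulates treatment-emergent events by severity, including Grade 5 (fatal), with no one-year limit visible. Listing 16.3.1.5 shows fatal events.

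**5. Long-term analysis set.** SAP 9.0 takes subjects with a Year 5 assessment. SAP 6.1 uses the All Treated Population for all safety and efficacy analyses. The two sections differ for any treated subject who leaves before Year 5, and the SAP does not say which one governs.

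**6. Share of follow-up.** SAP 9.0 places the long-term analysis at five years. Years 1 to 5 are (5 − 1)/5 = 80% of that time.

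**7. Illustration (assumed counts, not a forecast).** Suppose all 24 treated subjects complete Year 1 and four then leave because of AEs.
- 7.1.1 table: 0/24 premature terminations.
- Protocol 22.11 measure over all follow-up: 4/24 = 16.7%.
- Exact (Clopper-Pearson) 95% interval: lower limit = 2.5th percentile of Beta(4, 21) = 4.7%; upper limit = 97.5th percentile of Beta(5, 20) = 37.4%.

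The example applies to the 7.1.1 table only. If Table 14.1.3 covers all follow-up, the four subjects would appear there.

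**The case against.** The strongest reply is that Part 2 losses are not invisible. Tables 14.1.2 and 14.1.3 and their listings carry no one-year limit, days on study are uncapped, and fatal events are tabulated. SAP Section 7 also promises table shells detailed enough for programming, and these may define Table 14.1.3. This stands. A reader might infer that Part 2 drop-outs for harm have no planned summary at all, or that the one-year rule in 7.1.1 also governs Table 14.1.3. The documents support neither reading: 7.1.1 describes one disposition table, and nothing links its cut-off to the other tables. What remains is that a title alone fixes neither the period nor the reasons.

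A second reply is that withdrawal is not the only evidence on tolerability. The visible endpoint lists (Protocol 7.3.1, SAP 3.2.1) assess safety and tolerability by treatment-emergent events and changes, and the primary hypothesis rests on dose-limiting toxicity, which the SAP carries over. This also stands, and it rules out saying that tolerability would go unassessed. But Protocol 22.11 is the section headed tolerability, and the SAP does not reproduce its analysis.

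A third reply is that Protocol 22.1 lets the SAP modify the plan, and that curves in cohorts of 3, 3, 6 and 12 add little. By-cohort curves would indeed say little, and an overall curve may be enough. The permission does not explain a silent omission: 22.1 also requires major changes to an outcome measure or its analysis to appear in an amendment. Whether this change is major can be argued, but the visible SAP text does not address it.

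Some SAP endpoint text, the Part 1 time point in 22.11 and the short-term analysis time point are redacted. The analysis section headings and output lists that carry this point are readable.

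**Conclusion.** The point holds as a specification gap that should be closed. The SAP omits Protocol 22.11 without a stated reason. Its disposition table and flow diagram end at Year 1, and it specifies no AE-related or time-to-withdrawal summary for Part 2, about 80% of a five-year follow-up. SAP 9.0, read literally, also restricts the long-term analysis to subjects with a Year 5 assessment, which conflicts with SAP 6.1.

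The numerical effect cannot be known from the plan, because no drop-out rate is given in the visible text; the 4-of-24 case only shows how the 7.1.1 table would behave. The conclusion assumes that Part 2 begins at about the 1 Year Visit, that no redacted SAP text supplies the missing analysis, and that table shells not seen here do not already define Table 14.1.3. If the shells do define it by part and reason, the remaining gaps are the Kaplan-Meier curves, the one-year limit in 7.1.1 and the wording of 9.0.

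**What to change.** - Add a tolerability section to SAP 7.1 that carries over Protocol 22.11 for Part 1 and Part 2: number and percent discontinued due to AEs and for any reason, by cohort and overall, with death as its own reason.
- Add a Kaplan-Meier curve of time to withdrawal from implantation, overall at least, and state how deaths enter it. List the figure in Section 11.
- Extend 7.1.1 and the flow diagram to termination, reasons and completion at Year 5 as well as Year 1.
- Define Table 14.1.3 by part and by reason, with the number treated as denominator.
- State in 9.0 that all treated subjects stay in the long-term disposition and safety summaries whether or not they have a Year 5 assessment.
- If any part of 22.11 is to be dropped on purpose, give the reason, and consider whether Protocol 22.1 calls for an amendment.

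The cost is SAP wording, one figure and added rows in existing tables. On the visible text no new data are needed: Protocol Section 12 requires withdrawal reasons in the case report form and lists AE and death separately. The time point in that requirement is redacted, so the sponsor should confirm that reasons are also recorded for Part 2.

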### **7.1.2 Protocol Deviations**

A protocol deviation is any change, divergence, or departure from the study design or procedure defined in the protocol.

The following categories will be used to group protocol deviations:

1. Eligibility not met
2. Study Assessment Noncompliance
3. Other

The following are categorical reasons used to document why a protocol deviation occurred:

1. Subject illness
2. Clinical error
3. Investigator/staff decision
4. Other

A subset of the protocol deviations can be identified as an important protocol deviation as described below:

**Important Protocol Deviation:** An important protocol deviation that might significantly affect the completeness, accuracy, and/or reliability of the study data or that might significantly affect a subject's rights, safety, or well-being.

All documented protocol deviations in the study will be reviewed to identify all important protocol deviations by a data review team including representatives from clinical operations, medical, data management, and statistics.

A summary table of protocol deviations will be presented for the number and percentage of subjects in the following categories by cohort and overall:

- $\geq 1$  protocol deviation
- $\geq 1$  important protocol deviation
- Important protocol deviation category
- Important protocol deviation reason
- Protocol deviation category
- Protocol deviation reason

### 7.1.3 Demographics

A demographic and baseline characteristics table will be presented for the All Treated Population by cohort. The summary will include descriptive statistics for age, sex, race, weight, height, and BMI at baseline.

### 7.1.4 Medical and Surgical History

At the [REDACTED], the general medical and surgical procedures history will be recorded on the eCRF. Medical/Surgical History data will be summarized by Medical Dictionary for Regulatory Activities ([MedDRA](#)) version 25.0 System Organ Class (SOC) and Preferred Term (PT).

### 7.1.5 Concomitant Medications

All prior and concomitant medications, interventions and procedures will be tabulated. Prior and concomitant medications will be coded to the therapeutic drug classes and generic drug names using the World Health Organization Drug (WHODrug) classifications.

### 7.1.6 Adverse Events

The collection period for adverse events for the purposes of this protocol begins once the subject has signed the informed consent form and ends after the [REDACTED]. All adverse events will be listed by subject. The [MedDRA](#) (Version 25.0) will be used to classify all adverse events by SOC and PT.

A treatment emergent adverse event ([TEAE](#)) will be considered as any [AE](#) that starts on or after the date and time of the OpRegen administration, or if an [AE](#) that started before the OpRegen injection worsened after the administration of the investigational product.

A topline summary of treatment emergent adverse events with the number of events, number of subjects, and percentage of subjects for each category below will be tabulated by cohort.

- Any [TEAE](#) and [SAE](#)
- Subjects reporting at least one [TEAE](#) or [TE SAE](#) that is also related to OpRegen
- [TEAE](#) and [SAE](#) Severity: Grade 1/Mild, Grade 2/Moderate, Grade 3/Severe, Grade 4/Life Threatening/Disabling, Grade 5/Fatal
- Categories for all [TEAE](#) and with possible relationship to OpRegen

The following tables will be presented for the number of events by cohort:

- [TEAE](#) by preferred term sorted by descending number of overall events
- [TEAE](#) by SOC, PT\*
- [TEAE](#) by maximum severity\*
- [TEAE](#) by Possible Relationship to OpRegen\*

\*Subjects with >1 [AE](#) in respective category will only be counted once. For maximum severity tabulations, subjects will be counted once in the SOC and PT in the maximum severity.

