11.3.2.4 Surgical Procedure and Implantation of OpRegen®

The eye chosen for OpRegen® implantation will be the eye with worse visual acuity. The surgery will be performed by retro-bulbar or peribulbar anesthetic block or monitored intravenous sedation or by general anesthesia, at the discretion of the surgeon and in discussion with the subject. The eye undergoing surgery will be prepped and draped in sterile fashion according to the institutional protocol.

OpRegen® Subretinal Implantation with Vitrectomy

Vitrectomy procedure is required in the majority of cases in which retinal or sub-retinal intervention is performed. It is a routine procedure, with a low incidence of complications. The procedure involves formation of three small sclerotomies, removal of the vitreous gel, and then immediate implantation of the OpRegen® into the subretinal space via a very small caliber cannula.

The subretinal implantation as described following vitrectomy is schematically depicted in [Figure 3](#)²³ below.

[figure not shown]

Figure 3: Subretinal Implantation After Vitrectomy

A surgical procedure manual describes the details of the procedures for vitrectomy and OpRegen® subretinal implantation.

[figure not shown]
²³ From ([Stout JT 2011](#)). (Note that in this schematic drawing, placement of the surgical ports is not anatomically accurate).

Detailed surgical procedure manuals provided to the sites describe the specifics of the individual procedures. All surgical implantation procedures will be video-recorded for subsequent analyses.

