22.10 EVALUATION OF SAFETY

22.10.1 Treatment Emergent Adverse Events (TEAEs)

AEs will be recorded from the time a subject has signed the Informed Consent. All AEs reported by the investigators will be coded according to the current version of the MedDRA dictionary.

The following will be incorporated into the analysis of AEs:

- All analyses to be provided will include coded AEs.
- AEs analyses will include only the TEAEs, namely, those events which started following study IP implantation. Listings of both TEAEs and non-TEAEs will be provided.
- Summary tables of TEAEs will be provided by Study Cohort and overall.
- The incidence (no. of subjects) and frequency (no. of events) of TEAEs will be provided when broken down by System Organ Class (SOC) and by Preferred Term (PT) according to MedDRA dictionary.
- Breakdowns of TEAEs by all of the AEs attributes (e.g. seriousness, severity) will also be provided.
- Breakdowns of TEAEs by age and sex will also be provided.
- The derived dictionary used in the analyses displaying the MedDRA System Organ Class (SOC), the Preferred Term (PT), and the AE Verbatim Term as specified by the Investigator, will be provided.

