### 3.2 Study Endpoints

#### 3.2.1 Safety and Tolerability Endpoints

Safety and tolerability of OpRegen treatment will be assessed by:

- Incidence and frequency of treatment emergent adverse events ([AEs](#))
- Treatment emergent changes in the following variable:
  - Ophthalmological evaluation:
    - ✓ Intraocular Pressure ([IOP](#))

[REDACTED]

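### Protocol and SAP define treatment-emergent AEs differently, both start the clock at product administration although the operation begins earlier, and no AE-date rule settles events on the day of surgery

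*SAP*

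**What the plan says.** **Definitions.** Protocol 22.10.1 restricts AE analyses to "those events which started following study IP implantation". SAP 7.1.6 includes any AE "that starts on or after the date and time of the OpRegen administration" and adds a second limb for an AE "that started before the OpRegen injection worsened after the administration of the investigational product". The SAP does not say that it replaces the protocol definition.

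**Endpoint and outputs.** The first safety endpoint in SAP 3.2.1 is "Incidence and frequency of treatment emergent adverse events". SAP 7.1.6 plans "A topline summary of treatment emergent adverse events with the number of events, number of subjects, and percentage of subjects for each category below" and four further tables, all of TEAEs. The six AE tables in SAP Section 11 are also limited to TEAEs.

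**Listings.** SAP 7.1.6 states "All adverse events will be listed by subject", and Protocol 22.10.1 promises listings of TEAEs and non-TEAEs. The Section 11 index names three AE listings: TEAEs, SAEs and fatal outcomes.

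**Surgery.** Protocol 11.3.2.4 describes three sclerotomies, "removal of the vitreous gel, and then immediate implantation of the OpRegen® into the subretinal space". SAP 2.0 says that the second route also used a sclerotomy; its other steps are redacted. Protocol 14.1 assesses the safety of the surgical procedure during and after surgery, Protocol 21.1 records changes seen during surgery as AEs, and Protocol 21.2.1 allows device events present at surgery to be graded.

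**Dates.** Protocol 21.1.6 lists onset and resolution date among the CRF items and names no onset time. SAP 6.3 imputes incomplete dates under Section 4.1.1 to decide treatment emergence.

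**The concern.** In this trial the operation is part of what is being evaluated, so a complication between the first incision and the injection is a safety finding of interest. Under both definitions such an event falls before the starting point. Whether it reaches a summary table then depends on three things that the documents do not settle: which definition governs, whether a clock time exists, and what to do when it does not. Two programmers could produce different TEAE tables from the same data.

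The consequence is visible because the cohorts are small and because SAP Section 10 prints only categories in which a subject had a response and leaves 0% blank. If the omitted event is the only one of its kind, its row is simply absent.

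**Working it through.** The plan states no figure on this point, so there is nothing to reproduce. The check has three parts.

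**1. Apply each definition to hypothetical onsets.** Each case is classified by clock time and then by date alone. For the protocol, date alone means a date strictly after the day of implantation.

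| Onset | Protocol, time | Protocol, date | SAP, time | SAP, date |
|---|---|---|---|---|
| A. Surgery day, before injection, no worsening | no | no | no | yes |
| B. Surgery day, before injection, worsens after | no | no | yes | yes |
| C. At the moment of injection | no | no | yes | yes |
| D. Surgery day, after injection | yes | no | yes | yes |
| E. Day before, no worsening | no | no | no | no |
| F. Day before, worsens after injection | no | no | yes | yes |
| G. Day after | yes | yes | yes | yes |

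By clock time the documents disagree on B, C and F; by date alone they disagree on A, B, C, D and F. These counts describe the rules and say nothing about how often such events occur. Within the SAP, case A changes from excluded to included solely because the time is missing. Within the protocol, case D changes from included to excluded for the same reason. Rows B and F assume that worsening is not entered as a new AE.

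**2. Look for the missing rule.** SAP 4.1.1 defines study day, last study day and total days on study. Its only rule for a missing date concerns a subject's last study date. The redactions there sit where the day labels would be, and nothing visible suggests a hidden AE rule. The reference from SAP 6.3 therefore leads to no rule for AE onset.

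**3. Size per omitted subject.** Planned sizes are 3, 3, 6 and 12, total 24. If one subject's only event in a row is left out, the row changes by 100 × 1/n:

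- Cohort 1 or 2: 1/3 = 33.3 points
- Cohort 3: 1/6 = 16.7 points
- Cohort 4: 1/12 = 8.3 points
- Overall: 1/24 = 4.2 points

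Exact (Clopper-Pearson) two-sided 95% limits are given for scale only, since the SAP plans confidence intervals for efficacy endpoints. With zero events the upper limit is 1 − 0.025^(1/n).

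- Cohort 4: 1/12 = 8.3% (0.2 to 38.5) becomes 0/12, upper limit 1 − 0.025^(1/12) = 26.5%
- Overall: 1/24 = 4.2% (0.1 to 21.1) becomes 0/24, upper limit 1 − 0.025^(1/24) = 14.2%

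**The case against.** The case on the other side has real force.

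- **Exclusion needs a clock time.** Protocol 21.1.6 names only an onset date. On dates alone, the SAP counts every surgery-day event. This stands: exclusion is conditional, and a reader who infers that the SAP will hide surgical complications goes beyond the documents. The CRF itself is not among them, so neither branch can be ruled out.
- **The SAP may change the protocol's plan.** Protocol 22.1 allows this, so the difference is not in itself a breach. It still has to be stated, and it is not.
- **The worsening limb may matter little.** Protocol 21.1 treats a worsening condition as an AE. Entered as a new event, it would start after implantation under the protocol too. The gap narrows but does not close, because the documents do not say that worsening is entered that way.
- **Product administration is a coherent starting point**, and non-TEAEs are promised in listings. True, but the protocol also sets out to assess the operation, and Section 11 names no listing that would hold a non-serious non-TEAE.
- **Other outputs may show the event.** Table 14.1.5 and Listing 16.1.5 cover the surgical procedure, but their content is unspecified. A serious event would reach the SAE listing. It might also reach the topline table, where two of the four bullets say SAE without the treatment-emergent qualifier although the lead-in is limited to treatment-emergent events. Protocol 21.3.1 also sends Table 8 Grade 3-4 device events to expedited reporting.

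It is also tempting to treat two other features as errors: the absence of a table of Table 8 device events by grade, and the pooling of the two Cohort 4 delivery systems. The documents do not support that. Table 8 grading is optional, the SAP's five-grade scale is compatible with the protocol's general CTCAE rule, AE tables by cohort are what the protocol plans, and the device split is redacted.

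**Conclusion.** The point holds as an inconsistency and a missing rule, and should be corrected before database lock. The two definitions differ, neither covers the part of the operation before injection, and the rule that SAP 6.3 relies on does not exist. For a non-serious, non-worsening event before injection the result is exclusion from every TEAE table if time is recorded. If only a date is recorded, the event is probably included under the SAP and unclear under the protocol.

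The effect is 33.3, 16.7 or 8.3 points per affected subject by cohort and 4.2 overall, assuming that the subject has no other event in the row. The documents give no event timing or frequency, so the total effect is unknown and may be small. A reader might infer that dose-escalation safety is compromised. It is not: the stopping rules in Protocol 10.2 and the DLT definition in SAP 3.3 do not use the TEAE flag. This is a gap in reporting.

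**What to change.** 1. **Use one definition in both documents.** A TEAE is any AE that starts on or after the start of the study surgical procedure, or that started earlier and worsened on or after it. An AE dated on the day of surgery without a time, or with a partial onset date, counts as treatment-emergent unless the known part or the end date shows that it preceded surgery. Place this where SAP 6.3 points, and state that it replaces the wording in Protocol 22.10.1.
2. **Clarify the topline table.** Replace *Any TEAE and SAE* with separate lines for any TEAE, any treatment-emergent SAE, and any SAE since consent.
3. **Complete the index.** Add to Section 11 a title for the all-AE listing that both documents already promise.

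A table of Table 8 device events and descriptive Cohort 4 counts by delivery system, without tests, are optional additions.

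Cost: wording changes in both documents, one listing title and a slightly higher TEAE count. SAP 2.0 permits revision before database lock. The same-day default means that onset times need not be collected retrospectively.
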